2 INTRODUCTION

2.1 STUDY RATIONALE

Juvenile Idiopathic Arthritis (JIA)-associated uveitis and chronic anterior uveitis (CAU) can lead to significant vision loss early in life. Adalimumab, an anti-Tumor Necrosis Factor alpha (TNF- α) monoclonal antibody, is an effective treatment for refractory, JIA-associated uveitis and CAU. However, there are concerns regarding long-term adverse events associated with adalimumab treatment. In addition to possible detrimental effects of long-term treatment, the financial burden associated with adalimumab is a motivating factor for stopping treatment. There are no prospective studies examining uveitis recurrence rates after stopping adalimumab treatment in patients with JIA-associated uveitis or CAU who have achieved control of inflammation. Identifying potential predictors of recurrence of ocular inflammation could inform treatment decisions for personalized care. The potential for drug resistance further warrants the development of treatment guidelines. The results of this proposed study will provide evidence for the safety and utility of stopping adalimumab treatment in patients with JIA-associated uveitis or CAU.

2.2 BACKGROUND

Chronic, asymptomatic, anterior uveitis occurs in 12-38% of all patients with juvenile idiopathic arthritis (JIA) within 7 years of the onset of arthritis. 20-25% of all pediatric uveitis is associated with JIA.¹⁻³ There is significant evidence of poor long-term visual outcomes for JIA-associated uveitis, with as many as one third of all patients developing substantial visual impairment and 10-15% becoming legally blind.⁴⁻⁶

It is well-recognized that there is a chronic anterior uveitis phenotype in children that looks identical to chronic JIA-associated uveitis, but without the history of arthritis.⁷ Chronic anterior uveitis (CAU) does not have systemic manifestations of disease but presents similarly in the eye and can result in identical visual complications as JIA-associated uveitis. A large, population-based analysis using data from the National Paediatric Rheumatological Database in Germany showed that chronic anterior uveitis in children without arthritis appears to take a course similar to that of uveitis in patients with JIA and thus should be managed similarly.⁸ It is thought that the arthritis may not have been clinically detected since it is often mild in these patients, or that treatment that was initiated for uveitis masked the symptoms of arthritis. The European Medicines Agency (EMA) also considers pediatric chronic anterior uveitis without systemic symptoms to be comparable to JIA-associated uveitis from a treatment standpoint.⁹

While the primary interest of this study is JIA-associated uveitis, the inclusion of this secondary group of patients with chronic anterior uveitis (henceforth referred to as 'CAU') presenting with the same phenotype will increase generalizability and facilitate enrollment.

While methotrexate is the mainstay of long-term, immunomodulatory therapy for JIA-associated uveitis and CAU, previous studies have shown that anywhere from 15-50% of affected children will have refractory uveitis despite adherence to methotrexate treatment.¹⁰⁻¹³ Both human and animal models have suggested the pro-inflammatory cytokine TNF- α may play a role in both JIA and uveitis pathogeneses.¹⁴⁻¹⁶ Given its demonstrated efficacy in clinical trials, adalimumab has been approved by the U.S. Food and Drug Administration (FDA) for the treatment of both JIA and non-infectious intermediate, posterior, and panuveitis.¹⁷ Adalimumab has also been shown to effectively control inflammation in more than 80% of JIA-associated anterior uveitis cases, leading to its approval for use for this indication within the National Health System (NHS) in the UK.^{18,19}

Despite strong evidence for adalimumab's short-term efficacy for treating JIA-associated uveitis and CAU, there is a lack of evidence regarding long-term treatment outcomes for such patients.^{2,3,18-24} There is some evidence to suggest that patients on adalimumab may have higher rates of adverse events compared to patients on methotrexate alone.²⁵ In addition, anti-TNF- α therapy may harbor a risk of malignancy and opportunistic infection.²⁶⁻³⁴ These health concerns contribute to a growing interest in the possible cessation of adalimumab after a patient with JIA-associated uveitis or CAU has achieved disease control.

Anti-TNF- α therapy is expensive to the patient and healthcare system.^{35,36} A single dose of adalimumab costs £350 under NHS England.³⁶ A 2013 study found that, on average, a person with health insurance coverage in the U.S. pays \$26,537 for adalimumab in the first year of treatment.³⁷ Some patients may lose coverage for the drug, which may cause them to stop treatment for financial reasons. For example, the NHS England interim policy on anti-TNF- α treatment for pediatric uveitis mandates stopping treatment after 18 months and will discontinue financial coverage of adalimumab after this time.³⁸

While there is evidence to support the short-term effectiveness of treating JIA-associated uveitis and CAU with adalimumab, there have been no studies reporting on the ability to successfully taper or discontinue treatment when remission is presumed. There are limited data on discontinuation of other immunosuppressive treatments in JIA-associated uveitis and CAU. Data on withdrawal of immunomodulatory therapy in patients with JIA-associated uveitis or CAU and on discontinuation of anti-TNF- α treatment in patients with other autoimmune diseases both suggest a high relapse rate when stopping therapy after control of inflammation.³⁹⁻⁴⁷ Collectively, these studies suggest that discontinuation of adalimumab carries a risk of disease recurrence in patients with autoimmune conditions.

While there has yet to be any clinical trial on discontinuation of adalimumab in patients with JIA-associated uveitis or CAU, other observational studies have suggested that certain clinical characteristics such as duration of treatment or duration of inactive disease may be associated with likelihood of disease recurrence.^{39,47} In addition to use of clinical parameters to inform treatment decisions, there is interest in finding potential biomarkers that can predict disease relapse. Erythrocyte sedimentation rate (ESR) and C-reactive protein (CRP) levels in the blood serve as measures of non-specific, systemic inflammation and have been suggested as predictors of flare in JIA.^{48,49} The protein complex formed between MRP 8 and MRP 14 (calprotectin) has shown promise as a potential indicator of both relapse of rheumatic disease and response to anti-TNF- α treatment.⁵⁰⁻⁵⁴ Evaluating MRP8/14 serum levels in JIA-associated uveitis and CAU may uncover a key biomarker for ocular disease relapse or drug response that could inform ophthalmic treatment decisions.

Previous studies have found that between 9.2% and 32% of patients on adalimumab treatment developed antibodies against the drug.⁵⁵⁻⁵⁷ There is evidence to suggest that patients with uveitis who develop adalimumab antibodies may have worse ocular inflammatory outcomes compared to patients without these antibodies.⁵⁶ Furthermore, preliminary data on discontinuation of anti-TNF- α therapy have also raised concerns that patients may exhibit reduced sensitivity when retreated with the anti-TNF- α agent after disease recurrence.^{41,43} There are no published data addressing the safety of stopping adalimumab from an ocular standpoint, especially concerning development of reduced efficacy of anti-TNF- α therapy in the eye.

As the use of biologics in uveitis becomes increasingly common, questions regarding the safe and efficient use of anti-TNF- α therapy become increasingly relevant. In this multicenter, observer-masked, randomized clinical trial, we will compare rates of reactivation of ocular inflammation and adverse events

in patients with JIA-associated uveitis or CAU randomized to either continue their current treatment regimen of adalimumab or discontinue adalimumab. Addressing these clinically relevant research aims will provide a stronger evidence base for informing treatment guidelines for long-term use of adalimumab in patients with JIA-associated uveitis and CAU.

2.3 RISK/BENEFIT ASSESSMENT

2.3.1 KNOWN POTENTIAL RISKS

Based on product insert information,⁵⁸ the risks associated with adalimumab treatment include:

- Serious infections
- Reactivation of tuberculosis or new tuberculosis in patients with latent tuberculosis
- Malignancies
- Hypersensitivity reactions (localized rash, anaphylaxis, and angioneurotic edema)
- Injection-site pain
- Hepatitis B virus reactivation
- Neurologic reactions (multiple sclerosis, optic neuritis, peripheral demyelinating disease)
- Hematologic reactions (thrombocytopenia, leukopenia)
- Congestive heart failure
- Development of lupus-like syndrome (new formation of autoantibodies)
- Liver enzyme and creatinine elevations

Based on product insert information,⁵⁹ risks associated with methotrexate treatment include:

- Infection
- Nausea or vomiting
- Mild abdominal pain
- Dizziness
- Diarrhea
- Alopecia
- Leukopenia
- Elevated liver enzymes
- Potential for folic acid deficiency (patients should take folic acid supplements while on methotrexate)
- Rarely, an increased risk of severe opportunistic infection
- Rarely, an increased risk of cancer

Based on product insert information, risks associated with mycophenolate mofetil include:

- Infection
- Nausea or vomiting
- Mild abdominal pain
- Muscle aches
- Fatigue
- Diarrhea
- Hypertension
- Leukopenia

- Elevated liver enzymes
- Sepsis
- Rarely, an increased risk of severe opportunistic infection
- Rarely, an increased risk of cancer

Risks of treatment with placebo injection may include:

- Injection-site pain
- Localized rash

Risks of participating in the study include:

- Possible discomfort while undergoing eye exam
- Possible discomfort or bruising from venipuncture for lab tests

2.3.2 KNOWN POTENTIAL BENEFITS

Potential benefits for adalimumab treatment:

- Reduction in signs and symptoms of JIA or CAU
- Reduction in signs and symptoms of uveitis

Potential benefits for placebo treatment:

- Reduced exposure to adalimumab treatment and its associated risks of adverse events

2.3.3 ASSESSMENT OF POTENTIAL RISKS AND BENEFITS

Given the lack of information on the risk of recurrence of inflammation after stopping adalimumab, it is reasonable to expose participants to a treatment strategy of stopping therapy. The risks are particularly reasonable, given that patients must have achieved control of inflammation for at least 12 consecutive months while on adalimumab to be eligible for participation in the study.

Because JIA-associated uveitis and CAU are chronic diseases and standard clinical practice is to treat these conditions with long-term immunomodulatory therapy, it is reasonable to expose participants to continuing adalimumab treatment for up to 12 additional months. Adalimumab is FDA-approved in the same formulation and dosage as use in this trial for the indications of polyarticular JIA in children 2 years of age or older and for treatment of uveitis in adults. In addition, the NHS has approved adalimumab for the treatment of pediatric anterior uveitis and JIA-associated uveitis in the same formulation and dosage as used for this trial. Patients will be followed on a monthly basis and can stop treatment at any time if safety or tolerability issues arise that are suspected to be related to the study treatment.

This study will provide data on uveitis recurrence rates in patients with JIA-associated and CAU treated with adalimumab. Additionally, the study will provide further safety data on long-term use of adalimumab. The findings of this study will provide a stronger evidence base to inform safe and effective treatment strategies for patients with JIA-associated uveitis and CAU. The benefits of developing additional evidence-based clinical practice guidelines for this patient population outweigh the risks of participation.

3 OBJECTIVES AND ENDPOINTS

See the Statistical Analysis Plan (SAP) for details about the objectives, endpoints, and analysis.

3.1 TREATMENT FAILURE

Patients can discontinue the study treatment due to lack of efficacy and be declared a treatment failure if they have recurrence of ocular inflammation and/or recurrence of joint inflammation that is persistent and severe enough to necessitate unmasking to manage the arthritis recurrence.

Ocular inflammation is defined as ≥ 2 -step increase in AC cell from baseline, observed at 2 consecutive visits at least 7 days apart; $>0.5+$ AC cell for ≥ 28 days; $\geq 3+$ AC cell at a single visit; or $>0.5+$ vitreous haze, active retinal/choroidal lesions, or macular edema at a single visit.

Macular edema is defined as central subfield thickness on OCT > 2 standard deviations above normal thickness ($>320\mu\text{m}$ on Spectralis or $>300\mu\text{m}$ on Zeiss or Topcon) and having a greater than 20% increase from baseline *and/or* presence of intraretinal or subretinal fluid.

Patients with ocular inflammation that meets one of the treatment failure thresholds should return for an evaluation to evaluate whether the increased inflammation is sustained (called the Treatment Failure visit), as close to the 7- or 28-day period as possible, but no earlier.

Criteria for recurrence of ocular inflammation (at least one of the following in at least one eye)

Parameter	Definition
Anterior chamber cells*	≥ 2 -step increase** at two separate visits ≥ 7 days apart $>0.5+$ cell observed for ≥ 28 days $\geq 3+$ cell observed at a single visit
Vitreous haze***	$>0.5+$ haze at a single visit
Choroid & retina	Active retinal / choroidal inflammation and/or macular edema in either eye at a single visit. Macular edema is defined as central subfield thickness on OCT > 2 standard deviations above normal thickness ($>320\mu\text{m}$ on Spectralis or $>300\mu\text{m}$ on Zeiss or Topcon) and having a greater than 20% increase from baseline and/or presence of intraretinal or subretinal fluid

*SUN criteria; **increase is based on inflammation at baseline⁶⁰; ***NEI vitreous haze grading scale⁶¹

Patients who meet the treatment failure threshold of ocular inflammation at Month 12 will be re-evaluated after the Month 12 visit to assess for sustained inflammation which would result in treatment failure. If inflammation is sustained at the follow-up visit, then treatment failure is declared. At this point, patients and doctors will be unmasked, and doctors can treat per best medical judgement.

Patients in the placebo arm will be encouraged to restart adalimumab. The date of treatment failure is defined as the date of the initial visit when the ocular inflammation reached the threshold. A minimum of 90 days of follow-up is required following treatment failure, so if treatment failure is declared with fewer than 90 days remaining in the 12-month follow-up period, follow-up may be extended to up to 15 months. Regardless of the course of treatment pursued after treatment failure, all patients will be followed through Month 12 or a minimum of 90 days, whichever is longer.

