4.2 SCIENTIFIC RATIONALE FOR STUDY DESIGN

Justification for placebo treatment: As both patients and those assessing outcomes could introduce bias, complete masking of the treatment is ideal for this study. This concern is especially pertinent for the pediatric population, since it is difficult to prevent young patients from discussing their treatment with their physician. Our primary outcome is time to treatment failure, where treatment failure is defined as a recurrence of ocular inflammation (≥ 2 -step increase in AC cell observed at 2 consecutive visits at least 7 days apart; $>0.5+$ AC cell for ≥ 28 days; $\geq 3+$ AC cell observed at a single visit; or $>0.5+$ vitreous haze, active retinal/choroidal lesions, or macular edema at a single visit) and/or a recurrence of joint inflammation that is persistent and severe enough to necessitate unmasking to manage the arthritis recurrence. While an attempt will be made to ensure the grading of ocular inflammation is as standardized as possible, complete removal of subjectivity in inflammation grading is impossible. Furthermore, we plan to assess adverse events and quality of life as secondary outcomes, which rely on patient self-report. Given that self-report is involved in both the primary and secondary outcome assessments, masking of subjects is also necessary to remove any potential bias in assessing the outcomes for our study.

Justification for superiority: There is clinical utility in determining if one treatment plan is more effective for reducing the risk of recurrence of ocular inflammation. The findings of this trial could provide justification for either stopping adalimumab or continuing adalimumab for long-term management of JIA-associated uveitis and CAU, which are chronic conditions. Therefore, a superiority trial design is warranted.

Potential problems with placebo treatment: We hypothesize that stopping adalimumab will result in a shorter time to treatment failure and higher uveitis recurrence rates compared to continuing adalimumab. In anticipation of this possibility, we have allowed for patients to restart adalimumab or be treated per best medical judgement for the remainder of the study period. The primary analysis will be intent-to-treat, but we will also collect clinical outcome data at Month 12 to assess whether the initial strategy of stopping treatment results in worse outcomes compared to the initial strategy of continuing therapy.

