4.4 END OF STUDY DEFINITION

Participants are considered to have completed the study when they complete the Month 12 visit or the last scheduled procedure for the Month 12 visit as shown in the Schedule of Activities (SoA), **Section 1.3**. The end of the study is defined as completion of the last patient's visit or procedure shown in the SoA. Note that if inflammation is increased at Month 12 to a treatment failure criterion threshold, a follow-up visit must be conducted to determine whether the treatment failure criteria are met or not. If treatment failure is declared with fewer than 90 days remaining in follow-up, patients will be followed beyond Month 12 so that all patients have a minimum 90 days of follow-up after treatment failure. There will be a 90-day post-treatment failure study visit where the Clinical Eye Exam, Visual Acuity, OCT, and Adverse Event Report will need to be completed in addition to the Month 12 study visit. Standard of care labs will also be drawn only if the patient is on an antimetabolite and if more than 90 days have passed since their last standard of care lab draw. Follow-up could be extended up to 15 months if there is late treatment failure.

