2.3 Specific Aims

2.3.1 Specific Aim 1

Primary Outcome of the trial. The primary outcome for Specific Aim 1 will be time to treatment failure, with censoring at 12 months. Treatment failure occurs when recurrence of ocular inflammation is observed and/or the recurrence of joint inflammation is persistent and severe enough to necessitate unmasking to manage the arthritis recurrence. The recurrence of ocular inflammation is defined as one or more of the features in Table 1 in at least one eye:

Table 1: Criteria for Treatment Failure by Uveitis Recurrence
(at least one of the following in at least one eye)

Parameter	Definition
Anterior chamber cells*	≥2-step increase** at two separate visits ≥7 days apart >0.5+ cell observed for ≥28 days ≥3+ cell observed at a single visit
Vitreous haze***	>0.5+ haze at a single visit
Choroid & retina	Active retinal / choroidal lesions or macular edema (CST >2 standard deviations above normal thickness or cysts in 1mm central subfield) at a single visit

*SUN criteria³, **increase is based on inflammation at baseline; ***NEI vitreous haze grading scale⁴

Secondary Objectives

- To compare the proportion of people exhibiting treatment failure between the randomization groups during the first 6 months and during the first 12 months of study duration.
- To compare the cost-effectiveness of adalimumab therapy between the randomization groups during 12 months.

Secondary Objectives with Alternative Outcomes

We propose to compare longitudinal values of specific variables between the two randomization groups. The following outcomes will be compared:

- Best Corrected Visual Acuity (BCVA) score,
- Childhood Health Assessment Questionnaire score (CHAQ)⁵ in patients ages 5+,
- EuroQol 5 Dimension Youth Survey (EQ-5D-Y)⁶ score in patients ages 4+,
- Children's Visual Functioning Questionnaire (CVFQ)⁷ score in children aged 3 to 7 years,
- Effects of Youngster's Eyesight on Quality of Life (EYE-Q)⁸ score in children ages 5+,
- Juvenile Arthritis Disease Activity Score (JADAS)⁹ values: JADAS-10 and JADAS-27,
- Estimates of anti-adalimumab antibody (ADA) levels.

We also propose to compare proportions between the two randomization groups. These proportions correspond to the time until treatment failure or censoring time of 6 months as well as until treatment failure or censoring time of 12 months. Specifically:

- The proportion of patients who exhibit an arthritis flare, as defined in the Manual of Operations Section 6.4.1.²

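### The return-visit wording in Protocol 3.1, 4.4 and 7.1 does not exempt the four single-visit failure signs, so a sign seen at Month 12 that later clears could go undeclared

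*Protocol*

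**What the plan says.** **What counts as failure.** Protocol 3.1, 4.2 and 7.1 and SAP 2.3.1 (Table 1) list six ocular criteria. Two need persistence: a rise of at least 2 steps in AC cell at two visits at least 7 days apart, and AC cell above 0.5+ for at least 28 days. The other four count at one visit. For AC cell the level is 3+ or more. For haze, SAP Table 1 has ">0.5+ haze at a single visit". Protocol 4.2 ends its list with "active retinal/choroidal lesions, or macular edema at a single visit".

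**What happens at Month 12.** Protocol 3.1, repeated in 7.1: "Patients who meet the treatment failure threshold of ocular inflammation at Month 12 will be re-evaluated after the Month 12 visit". Then: "If inflammation is sustained at the follow-up visit, then treatment failure is declared". Then: "At this point, patients and doctors will be unmasked, and doctors can treat per best medical judgement". Section 4.4 says that if inflammation reaches a criterion threshold at Month 12, "a follow-up visit must be conducted to determine whether the treatment failure criteria are met or not".

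**What happens at any visit.** A general sentence in 3.1 and 7.1 sends patients who meet any one of the thresholds back to check whether the inflammation is sustained. In 3.1 this visit is timed "as close to the 7- or 28-day period as possible, but no earlier".

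**Which document governs the endpoint.** Protocol 3: "See the Statistical Analysis Plan (SAP) for details about the objectives, endpoints, and analysis". The SAP has no Month 12 confirmation step.

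**The concern.** For a single-visit sign, the criterion is already met on the day it is seen. An instruction to return and find out whether it is met therefore conflicts with the definition. None of the three sections says that the return visit is only for the two persistence criteria.

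What is at stake is mainly what declaration sets in motion. Sections 3.1 and 4.4 require at least 90 days of follow-up after failure. Footnote g of the Schedule of Activities (1.3) extends open-label adalimumab to Month 15 when failure occurs at Month 12, whereas routine dispensing ends before Month 12. A patient on placebo with 3+ cells or macular edema at Month 12 that has cleared by the return visit could receive neither. The event could also be missing from the site's declarations although SAP Table 1 counts it.

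**Working it through.** **1. The texts side by side**

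| Sign | Protocol 3.1 and SAP Table 1 | Month 12 text, read literally |
|---|---|---|
| AC cell rise of ≥2 steps | two visits, ≥7 days apart | return visit (consistent) |
| AC cell >0.5+ | ≥28 days | return visit (consistent) |
| AC cell ≥3+ | one visit | return visit (conflict) |
| Vitreous haze >0.5+ | one visit | return visit (conflict) |
| Active retinal/choroidal lesions | one visit | return visit (conflict) |
| Macular edema | one visit | return visit (conflict) |

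The 7- and 28-day intervals belong to the first two rows. The text gives no return interval for the other four.

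**2. The planning figure reproduces**

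Inputs from SAP 3.3.1: medians of 10 weeks (stop) and 20 weeks (continue), 59 per arm, 10% loss, two-sided alpha 0.05, 88% power. Follow-up is 48 weeks (Protocol 1.1).

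- λ = ln 2 / median: 0.0693 (stop) and 0.0347 (continue) per week.
- SAP formula: N per arm = (Zα + Zβ)² × [φ(λ stop) + φ(λ continue)] / (λ stop − λ continue)², with φ(λ) = λ² / (1 − exp(−48λ)). This gives 52.9.
- 52.9 / 0.9 = 58.8, so 59 per arm and 118 in total, as stated.

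**3. How many first failures fall at Month 12**

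Assumptions: exponential failure and loss times; failures first seen at Month 12 arise between the Month 10 visit (week 40) and week 48. Loss rate η = −ln(0.9)/48 = 0.0022 per week.

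P = λ/(λ+η) × [exp(−40(λ+η)) − exp(−48(λ+η))]

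- Stop: 0.0242 × 59 = 1.43. Continue: 0.0550 × 59 = 3.24. Total 4.67, or 4.0% of 118.
- With no loss: 1.57 + 3.57 = 5.14.
- If the continue arm instead follows the figure cited in SAP 3.3.1 of 90% inactive at week 54: λ = 0.00195, 0.77 patients, and a total of about 2.2.

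These totals include every type of failure. The share that are single-visit signs which then clear is not given. From 0% to 100%, the range is 0 to 4.7 patients.

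Only macular edema has a planning figure: at most 1% in the continue arm, with a detectable difference of 15 points (SAP 3.3.2.1). Taking that difference as real gives 16% in the stop arm. If edema follows the timing of failure, the weeks 40–48 share of events is 1.43/55.3 = 2.6% (stop) and 3.24/46.0 = 7.0% (continue). Then 59×0.16×0.026 + 59×0.01×0.070 = 0.3 patients. Spread evenly over 48 weeks: 59×0.17×8/48 = 1.7.

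**4. Effect on the estimates**

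Dropping every Month 12 event in both arms removes the last event time from the Cox partial likelihood. The estimate then rests on data through Month 10, and under proportional hazards it should not shift. A simulation agrees. It used 2,000 trials with 59 per arm, failures detected at the scheduled visits, Efron ties and loss censored at the last visit.

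| Month 12 events dropped | Hazard ratio (geometric mean) |
|---|---|
| none | 2.01 |
| all, both arms | 2.01 |
| random half | 2.01 |
| continue arm only | 2.09 |
| stop arm only | 1.92 |

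A repeat with different random numbers agreed to within 0.01.

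The secondary 12-month failure proportion moves more. Expected failures by week 48 are 55.3 and 46.0, a risk ratio of 1.20. With all Month 12 events dropped it is (55.3 − 1.43)/(46.0 − 3.24) = 1.26.

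Power, from Φ(½√d × ln 2 − 1.96), falls from 88.8% at the 84 events in SAP 3.7 to 87.0% at 84 − 4.7 = 79.3.

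**The case against.** **The narrower reading is probably the intended one.** The return visit is timed to 7 or 28 days. Section 4.4 separates reaching a threshold from meeting the criteria, and that distinction has content only for the persistence criteria. The single-visit table stands just above the Month 12 sentences in 3.1. Those sentences say that failure is declared if inflammation is sustained; they do not say only if. All of this stands, and it makes the point a gap in wording. It does not remove the gap, since three sections give the instruction and none limits it.

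**A reader might infer that unmasking and treatment must wait.** The documents do not support that. Protocol 8.2 and SAP 3.1.1 provide for unmasking at Month 12 or at failure. Section 6.1.2 lets either arm stop treatment at any time for efficacy and be treated at the physician's judgement. Section 6.5.1 leaves treatment of macular edema to the investigator, and 7.1.1 allows emergency unmasking. Section 6.5.3 makes extra corticosteroid a recordable deviation and does not forbid it.

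**Under-declaration may be recoverable.** Eye examination and OCT are recorded at each visit, a form-schedule footnote in 1.3 allows declaration at any visit, Protocol 10.1 gives the Coordinating Center event adjudication, and 10.1.6 promises full verification of the data. This could restore the event for analysis, although no adjudication procedure is described. It could not restore follow-up or drug supply that was never started. The Manual of Procedures may also settle the matter for sites, but it is not among the documents.

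**Conclusion.** The point holds as an inconsistency between the instruction to sites and the endpoint definition, and it is worth correcting. Its practical consequence is that a single-visit sign at Month 12 that clears may go undeclared, so that the 90-day follow-up and open-label drug are not triggered. This is a risk from the wording; nothing in the documents shows that it has happened.

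The reach is an upper bound of about 4.7 of 118 patients (5.1 without loss, 2.2 with a low failure rate in the continue arm). It rests on exponential times and the planning medians, and it counts all failure types. It covers Month 12 only. The general return-visit sentence has the same gap at earlier visits, but it does not itself make declaration depend on sustained inflammation, and its reach cannot be estimated from the documents.

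A reader might infer that the primary result is in doubt. It is not: the hazard ratio is essentially unchanged if Month 12 events are lost from both arms, and lies between 1.92 and 2.09 if all are lost from one arm only.

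A reader might also infer that the SAP settles the analysis definition completely. For macular edema it does not. Protocol 3.1 requires thickness above the limit together with an increase of more than 20% from baseline, and/or intraretinal or subretinal fluid. SAP Table 1 accepts thickness above the limit, or cysts in the central subfield, with no change from baseline.

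**What to change.** In Protocol 3.1, 4.4 and 7.1, limit the return visit and the sustained-inflammation condition to two criteria: the AC cell rise of ≥2 steps (≥7 days apart) and AC cell >0.5+ (≥28 days). State that the four single-visit signs are declared at the visit where they are seen, including Month 12.

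Do not reclassify recorded Month 12 cases mechanically against SAP Table 1 unless its macular edema definition is first aligned with Protocol 3.1. Otherwise a patient with a thick macula at baseline and little change could become a failure that the protocol would not count, in the primary endpoint and after the interim unmasking.

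The cost is a minor wording amendment. It reaches only patients still in follow-up, because enrollment stopped on 14 February 2024 (Protocol 10.1.12.5). Any additional Month 12 failure uses the 90-day visit and open-label supply that the protocol already provides.
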